9.4.1 Adverse Events

For analysis purposes, AEs will be classified as pretreatment AEs, TEAEs during the Ivacaftor Run-in Period, TEAEs during the Active Comparator Treatment Period, or post-treatment AEs, defined as follows:

- **Pretreatment AE:** any AE that started before initial dosing of study drug in the Ivacaftor Run-in Period.
- **TEAEs during the Ivacaftor Run-in Period:** any AE that increased in severity or that was newly developed at or after initial dosing of study drug through the end of the TE Period for the Ivacaftor Run-in Period.
- **TEAEs during the Active Comparator Treatment Period:** any AE that increased in severity or that was newly developed at or after initial dosing of study drug through the end of the TE Period for the Active Comparator Treatment Period.
- **Post-treatment AEs:** any AE that increased in severity or that was newly developed beyond the TE Period.

For AEs with a missing or partial start date, if there is no clear evidence that the AEs started (or increased in severity) before or after the first dose date for the Active Comparator Treatment Period, the AE will be considered to be a TEAE for the Active Comparator Treatment Period (see Section 11.7). If there is clear evidence that the AE started before the first dose date for the Active Comparator Treatment Period, but there is no clear evidence

that the AE started before or after the first dose date for the Ivacaftor Run-in Period, the AE will be considered to be a TEAE for the Ivacaftor Run-in Period. Similarly, if there is no clear evidence that the AEs started (or increased in severity) before or after the start of the post-treatment period, the start date will be imputed to be the earliest possible time in the TEAE period and the AE will be considered to be a TEAE.

Unless otherwise stated, all TEAE summaries will be provided separately for the Ivacaftor Run-in Period and the Active Comparator Treatment Period. Presented percentages will be calculated based on the number of subjects in the Safety Set of the corresponding period.

Based on the reported severity and relationship to study drugs, TEAEs can be categorized as follows:

By relationship to the study drugs, treatment emergent adverse events (TEAEs) will be classified into 4 categories:

- Not related
- Unlikely related
- Possibly related
- Related.

By severity, TEAEs will be classified into 4 categories:

- Mild (Grade 1): Mild level of discomfort and does not interfere with regular activities
- Moderate (Grade 2): Moderate level of discomfort and significantly interferes with regular activities
- Severe (Grade 3): Significant level of discomfort and prevents regular activities
- Life-threatening (Grade 4 and 5): Any adverse drug experience that places the subject, in the view of the investigator, at immediate risk of death.

9.4.1.1 Overview of TEAEs

An overview of the TEAE profile will be provided for the total number of TEAEs, and with number and percent of subjects including the following categories:

- All TEAEs
- Serious TEAEs
- Grade 3/4 TEAEs
- TEAEs by relationship
- TEAEs by severity
- TEAEs leading to death
- TEAEs leading to treatment discontinuation
- TEAEs leading to treatment interruption

Note that per protocol, ‘Neither the dosage of individual study drugs nor the combination therapy can be altered, but the investigator can interrupt or stop

treatment with all study drugs' (section 10.4 of protocol). In the rare event when there are different actions applied to VX-661 100-mg/IVA 150-mg fixed-dose tablet (FDC) and to IVA 150-mg tablet, TEAEs leading to treatment discontinuation will include TEAEs leading to withdrawn of both FDC and IVA tablets, or either FDC or IVA tablets. TEAEs leading to treatment interruption will include TEAEs leading to drug interruption for both FDC and IVA tablets, or either FDC or IVA tablets.

9.4.1.2 TEAEs by System Organ Class (SOC) and Preferred Term (PT)

Summaries will be presented by MedDRA system organ class (SOC) and preferred term using frequency counts and percentages (i.e., number and percentage of subjects with an event). When summarizing the number and percentage of subjects with an event, subjects with multiple occurrences of the same AE or a continuing AE will be counted once. Only the maximum severity level will be presented in the severity summaries, and the strongest relationship level will be presented in the relationship summaries.

Additional summary tables may be presented for TEAEs in the Active Comparator Treatment Period only, showing number and percentage of subjects

- Any TEAE by PT
- TEAE with a frequency of $\geq 5\%$ in any treatment group by PT (Active Comparator Treatment Period)
- TEAE with a frequency of $\geq 5\%$ in any treatment group by SOC and PT (Active Comparator Treatment Period)
- TEAEs of $\geq 2\%$ more frequent at the PT level in the VX-661/ivacaftor combination therapy than ivacaftor monotherapy, by PT
- TEAEs of $\geq 2\%$ more frequent at the PT level in the VX-661/ivacaftor combination therapy than ivacaftor monotherapy, by SOC and PT

9.4.1.3 Respiratory Events and Symptoms

Respiratory symptoms are defined as any TEAEs for the following 3 PTs:

- Chest discomfort
- Dyspnoea
- Respiration abnormal

Respiratory events are defined as any of the afore-mentioned respiratory symptoms, or any TEAEs for the following 4 additional PTs:

- Asthma
- Bronchial hyperreactivity
- Bronchospasm
- Wheezing

A summary of respiratory symptoms and events will be presented by preferred term.

9.4.1.4 Subgroup Analysis

TEAE summaries in the Active Comparator Treatment Period will also be presented by SOC and PT for the following subgroups:

- Age group at screening (<18, and ≥18 years)
- Percent predicted FEV₁ severity at the end of Ivacaftor Run-in Period as a stratification factor per IWRS (<70, and ≥70)
- Region (North America and Others)
- Type of mutation on the second *CFTR* allele (*R117H* versus others)

In addition, a listing containing individual subject adverse event data for TEAEs leading to treatment discontinuation, TEAEs leading to treatment interruption, SAEs and all deaths will be provided separately, with a flag indicating the TEAE status for SAEs and deaths.

9.4.1.5 Clinical Laboratory

The analysis of clinical laboratory measurements will be presented separately for the Ivacaftor Run-in Period and by treatment group at each scheduled time point for the Active Comparator Treatment Period based on the corresponding Safety Set.

For treatment-emergent laboratory measurements, the raw values and change from baseline values of the continuous hematology and chemistry results, including coagulation studies will be summarized in SI units by treatment group and visit.

The number and percentage of subjects with at least 1 potentially clinically significant (PCS) laboratory event during the TE period will be summarized overall and by treatment group, including the shift of the PCS event from baseline to postbaseline. The PCS criteria are provided in [Appendix I](#).

For each liver function test (LFT) laboratory test (alanine aminotransferase [ALT], aspartate aminotransferase [AST], alkaline phosphatase [ALP], gamma-glutamyl transferase [GGT], and total bilirubin), the following additional analyses will be conducted for the Active Comparator Treatment Period:

- A listing of subjects with elevated LFT results during the TE period will be presented. For each subject in the listing, LFT assessments at all time points will be included (scheduled and unscheduled).
- For each of the LFTs, mean values (±SD) will be plotted by visit, and a box plot of the LFT value/ULN will be plotted by visit.
- The incidence of LFTs meeting threshold criteria
- For each of the LFTs, mean values (±SD) will be plotted by visit, and a box plot of the LFT value/ULN will be plotted by visit.
- The incidence of LFTs meeting threshold criteria against the baseline threshold criteria also will be summarized by treatment group, LFT parameters, and visit (only shifts to values worse than baseline will be presented).

- A scatter plot of the maximum ALT value across visits versus the maximum total bilirubin value also will be presented. The ALT and total bilirubin values will be presented on a logarithmic scale. The graph will be divided into 4 quadrants with a vertical line corresponding to 3xULN for ALT and a horizontal line corresponding to 2xULN for total bilirubin. A similar graph of maximum AST value versus maximum total bilirubin value will be presented as well.

For the Active Treatment Period, a summary table for the shift from baseline to the value at Week 8 will be presented by treatment group for vitamin levels and lipid panel. A box plot of vitamin levels and lipid panel also will be plotted against visit.

In addition, a listing containing individual subject hematology, chemistry, and coagulation values outside the normal reference ranges will be provided. This listing will include data from both scheduled and unscheduled visits. Subject with positive pregnancy test results will be listed. Abnormal urinalysis results will also be listed in individual subject data listings.

9.4.2 Electrocardiogram

For treatment-emergent ECG measurements, a summary of raw values and change from baseline values for the Active Treatment Period will be provided by treatment group and visit for the following standard 12-lead ECG measurements: RR (ms), HR (bpm), PR (ms), QRS duration (ms), QRS axis (degrees), QT (ms), and QT corrected for HR intervals [QTcF (ms)].

The number and percentage of subjects with at least 1 PCS ECG event during the TE period will be summarized by treatment group and ECG parameters. The PCS criteria are provided in [Appendix I](#).

9.4.3 Vital Signs

The raw values and change from the corresponding treatment period baseline values will be summarized at each scheduled time point during the TE Period based on the corresponding Safety Set in the Ivacaftor Run-in Period and by treatment group in the Active Comparator Treatment Period: systolic and diastolic blood pressure (mm Hg), body temperature ($^{\circ}$ C), pulse rate (beats per minute [bpm]), and respiratory rate (breaths per minute).

9.4.4 Physical Examination

Physical examination findings will be presented as an individual subject data listing only.

9.4.5 Pulse Oximetry

The raw values and change from the corresponding treatment period baseline values will be summarized at each scheduled time point during the TE Period based on the corresponding Safety Set for the Ivacaftor Run-in Period and by treatment groups for the Active Comparator Treatment Period, separately. In addition, the mean value at each visit during the TE Period will be plotted by treatment group for the Active Comparator for the percent of oxygen saturation.

9.4.6 Postdose Spirometry

For the 2-hour and 4-hour postdose spirometry measurements on Day 1 and Day 15, a summary of raw values for percent predicted FEV1 will be provided by treatment group at each time point. The absolute change from the predose value of percent predicted FEV1 on the same day will be provided by treatment group at each time point. In addition, a boxplot by time point will be provided. Within each treatment group, Day 1 and Day 15 values will be presented on the same plot.

The above analyses will be repeated for FEV1.

In addition, the number and percentage of subjects with percent predicted FEV1 decline ≥ 10 , ≥ 15 , and ≥ 20 percentage points in the absolute change from the predose value will be summarized by treatment group and by assessment day and time.

9.4.7 Ophthalmology Examination

Ophthalmologic findings (cataracts) during the treatment-emergent period will be summarized by treatment group. The numbers and percentages of subjects with a cataract at screening will be presented. The numbers and percentages of subjects with a cataract after the first dose of study drug will be presented.

In addition, ophthalmology examination results will be provided in a data listing for subjects who have developed any cataracts during the treatment-emergent period. Subjects with cataract at screening will also be listed.

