### 11.7.8 Ophthalmologic Examination

Subjects will undergo an ophthalmologic examination performed by a licensed ophthalmologist at screening, which includes

- measurement of best corrected distance visual acuity of each eye;
- measurement of lens refracting power following cycloplegia (e.g., autorefractor or ophthalmoscopy streak); and
- pharmacologically dilated examination of the lens with a slit lamp.

The screening ophthalmologic examination must be completed and the results reviewed before enrollment. This examination does not have to be repeated if there is documentation of an examination that met protocol criteria and that was within 3 months before the start of the Screening Period or if there is documentation of bilateral lens removal.

If a cataract, lens opacity, Y-suture, or lamellar rings are identified and determined to be clinically significant by the ophthalmologist at the Screening examination, the subject is ineligible for study entry (Section 9.2). If a cataract or lens opacity is identified and determined to be clinically significant by the ophthalmologist after dosing, the subject and Vertex medical monitor will be notified. After discussion with the principal investigator, who collaborates with the Vertex medical monitor, the subject may elect to continue or discontinue study drug treatment. If the subject discontinues study drug treatment, the subject should complete the ETT Visit, all subsequent scheduled visits per Table 3-2, and the Safety Follow-up Visit (see Sections 8.1.4 and 8.1.5). If the subject continues study drug treatment, more frequent ophthalmologic monitoring should be considered.

In addition to the Screening Visit, an ophthalmologic examination will be performed by a licensed ophthalmologist at the Safety Follow-up Visit or ETT Visit for the following subjects:

- subjects <18 years of age at the Screening Visit who discontinue study drug treatment after receiving at least 1 dose of study drug,
- subjects <18 years of age at the Screening Visit who complete study drug treatment but do not enroll in a separate extension study of VX-661/ivacaftor within 28 days after the last dose of study drug.

This examination may be completed at either the ETT Visit or Safety Follow-up Visit, but must be completed by the date of the Safety Follow-up Visit.

Subjects  $\geq 18$  years of age at the Screening Visit are not required to complete ophthalmologic examinations at the ETT Visit or Safety Follow-Up Visit.

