8.3 Safety Set

The **Safety Set**, defined separately for the **Ivacaftor Run-in Period** and the **Active Comparator Treatment Period**, includes all subjects who received at least 1 dose of study drug in the corresponding treatment period. The safety analyses will be performed separately for the Ivacaftor Run-in Period and the Active Comparator Treatment Period; subjects will be analyzed according to the treatment they received.

For the safety analysis, the following analyses period will be defined as below:

- The **pre-treatment period (Ivacaftor Run-in Period only)** is defined as the period after the informed consent/assent date and before the initial dosing of study drug in the Ivacaftor Run-in Period.
- The **Treatment-emergent (TE) Period** will be defined separately for the Ivacaftor Run-in Period and the Active Comparator Treatment Period:
 - The TE Period for the Ivacaftor Run-in Period is defined as the date of the first dose in the Ivacaftor Run-in Period to 1) the last day prior to the first dose of the Active Comparator Treatment Period or 2) either the Safety Follow-up Visit or 28 days (inclusive) after the last dose, whichever is earlier, for subjects who discontinue treatment during the Ivacaftor Run-in Period and are not randomized in the Active Comparator Treatment Period.
 - The TE Period for the Active Comparator Treatment Period is defined as the first dose of the Active Comparator Treatment Period to the Safety Follow-up Visit or 28 days (inclusive) after the last dose, whichever is earlier, in the Active Comparator Treatment Period.

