9.4 Safety Analysis

Safety endpoints will be analyzed separately for the Ivacaftor Run-in Period and the Active Comparator Treatment Period based on the corresponding Safety Set. Only descriptive summaries of safety will be provided (i.e., no statistical testing will be performed).

The overall safety profile of study drug will be assessed in terms of the following safety and tolerability endpoints:

- Adverse events
- Clinical laboratory values (hematology, serum chemistry, coagulation studies, and urinalysis)
- Standard 12-lead electrocardiograms
- Vital signs
- Pulse oximetry

The safety profile will also include the following safety-supporting data

- Weight
- BMI
- Ophthalmological Examination

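### The post-dose cataract percentage in SAP 9.4.7 falls by default on the Safety Set, most of whom have no scheduled post-dose lens examination, so it understates the rate

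*SAP*

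**What the plan says.** SAP 9.4.7 plans a by-arm summary of cataract findings, one percentage at screening and one after dosing. For the latter: "The numbers and percentages of subjects with a cataract after the first dose of study drug will be presented". The section gives no denominator and does not ask for the number of subjects examined.

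The only rule in the SAP that reaches this section is the general one in 9.4: "Safety endpoints will be analyzed separately for the Ivacaftor Run-in Period and the Active Comparator Treatment Period based on the corresponding Safety Set". Section 9.4 includes the ophthalmologic examination among its safety-supporting data. Under SAP 8.3, the Safety Set "includes all subjects who received at least 1 dose of study drug in the corresponding treatment period". Having been examined is not a condition.

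Protocol 11.7.8 sets out who has a lens examination after dosing. There are two groups. The first is "subjects <18 years of age at the Screening Visit who discontinue study drug treatment after receiving at least 1 dose of study drug". The second is those of the same age who finish treatment without joining the extension in the following 28 days. Subjects aged 18 or over "are not required to complete ophthalmologic examinations at the ETT Visit or Safety Follow-Up Visit". Subjects with documented bilateral lens removal are exempt. Further examinations may be done at the investigator's discretion. The schedule footnotes in Protocol Table 3-2 and SAP Appendix C repeat the under-18 rule.

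**The concern.** A percentage of subjects with a finding can be read as a rate only if the people in the denominator were looked at. Here the default denominator is everyone dosed, while the protocol schedules the examination for a small subset. A subject who was not examined cannot enter the numerator through that examination, yet stays in the denominator and so counts as free of cataract.

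A result such as 0 of 80 would look like evidence on lens safety that the trial did not collect. The contrast with the screening percentage makes this worse. Screening examinations cover all ages, apart from subjects with a recent documented examination or bilateral lens removal, so that percentage rests on near-complete data. Placing the two percentages side by side on the same denominator invites a before-and-after comparison that the data cannot support.

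The protocol takes the lens seriously: clinically significant opacities exclude a subject at entry, and a cataract or lens opacity on treatment is a listed reason for possible withdrawal. Readers will look at this table.

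**Working it through.** The documents state no cataract rate and no expected number of post-dose examinations, so there is no planned figure to reproduce. The check shows how far the percentage moves with the denominator.

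**Inputs from the documents**
- About 160 subjects randomized 1:1 (SAP 7.1), so 160 / 2 = 80 per arm. The Safety Set is taken as about 80 per arm, assuming nearly all randomized subjects are dosed.
- Scheduled post-dose examination: under 18 at screening, and either stopped treatment or completed it without entering the extension within 28 days (Protocol 11.7.8).

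**Inputs not in the documents, assumed as ranges**
- a, the share under 18: 10% to 40%.
- b, the share of those who stop or do not roll over: 5% to 30%.
- A true rate of 5%, used only to show the dilution.

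**Formulas**
- Scheduled examinations per arm = 80 × a × b.
- Percentage on the Safety Set = true rate × a × b. This assumes that cataracts are found only at scheduled examinations and are equally common in examined and unexamined subjects.

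| a | b | Scheduled examinations per 80 | A true 5% reads as |
|---|---|---|---|
| 10% | 5% | 0.4 | 0.025% |
| 20% | 10% | 1.6 | 0.10% |
| 30% | 20% | 4.8 | 0.30% |
| 40% | 30% | 9.6 | 0.60% |
| 10% | 100% | 8 | 0.5% |
| 40% | 100% | 32 | 2.0% |

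In the first four rows the examined fraction runs from 0.5% to 12%, a dilution of 1/0.005 = 200 times down to 1/0.12 = about 8 times. The last two rows are a deliberate extreme in which every under-18 is examined. Even then the percentage is too low by a factor of 2.5 to 10, because adults have no scheduled examination.

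**What zero cases would mean.** With no events in n examined subjects, the exact one-sided 95% upper bound is 1 − 0.05^(1/n):
- n = 80: 3.7%
- n = 8: 31%
- n = 2: 78%

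A reader who takes 0/80 at face value would rule out rates above about 4%. If 8 or 2 subjects were actually examined, the data would be compatible with rates up to 31% or 78%.

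**The case against.** The best counter-argument is that the SAP never says unexamined subjects count as negative. Section 9.4.7 names no denominator. The adverse event section does state that its percentages use the number in the Safety Set, so silence here could be deliberate. SAP 9.1 says missing data are not imputed, and counting an unexamined subject as cataract-free amounts to imputation. Section 9.4.6 uses similar wording for post-dose spirometry, which is done only in under-18s. On this view the denominator is merely unspecified.

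What stands is that the Safety Set denominator comes from the general rule, not from 9.4.7 itself. But that is the only rule the SAP supplies for this section, and a programmer following it would divide by the Safety Set. If the sponsor intends the number examined, the SAP has to say so, and the same edit is needed.

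It is also true that this is descriptive supporting data, that no test depends on it, and that listings will show the subjects who developed cataracts. That limits the weight of the point. It does not correct the percentage.

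A reader might infer that adults and rollover subjects are never re-examined. The documents do not support that. Protocol 11.7.8 allows discretionary examinations, and a clinically evident cataract in any enrolled subject can be reported as an adverse event (Protocol 13.1.1.3). Such findings add cases from a selected group, but they do not make the rest of the denominator examined.

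**Conclusion.** The concern holds as a denominator problem. Followed as written, the plan yields a by-arm percentage in which most subjects had no scheduled post-dose lens examination, so the proportion with a cataract is understated unless discretionary examinations are widespread.

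The size cannot be fixed from the documents, which give neither the share under 18 nor the rollover rate. The 0.4 to 9.6 scheduled examinations per 80 is an illustration under the stated ranges. Two other readings go too far:
- That a particular handful of subjects per arm will be examined. This depends on shares the documents do not contain.
- That the percentage among examined subjects is the trial's cataract incidence. Those subjects either stopped treatment or did not roll over. In addition, only clinically significant lens findings are excluded at entry, so a minor cataract already present could be counted after dosing.

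Nor do the documents say that the extension study performs eye examinations, so the gap cannot be assumed to be filled there. The point concerns one safety table and does not touch the primary endpoint. It should be corrected before database lock.

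**What to change.** Amend SAP 9.4.7 and its table shell as follows:
1. Print, per arm, the number of subjects with at least one ophthalmologic examination after the first dose in the Active Comparator Treatment Period, excluding those with bilateral lens removal.
2. Use that number as the denominator for the post-dose cataract percentage.
3. Add a footnote that adults, and under-18 completers who entered the extension within 28 days, had no scheduled post-dose examination in this study. State also that the examined group is selected, so the percentage is not an incidence for the trial population.
4. Make no statement about eye assessments in the extension study, since the documents do not describe them.

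The examination window should be the same for numerator and denominator. SAP 8.3 ends the treatment-emergent period no later than 28 days after the last dose, while the Safety Follow-up Visit may fall as late as day 28 + 7 = 35. An examination on days 29 to 35 would otherwise drop out of the treatment-emergent summary.

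The cost is SAP wording and one table shell, with no new procedure or data collection. The drawback is that the percentage will rest on a small, selected group and be imprecise, but the printed number examined makes that visible.
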